4.3.2 Secondary Efficacy Analyses

Additional lesion count presentations will be presented as described in the protocol.

Investigator's global assessment will be presented as described in the protocol.

Treatment success derived from IGA will be tabulated and tested by a McNemar's test. This is a minor deviation from the protocol where a Fisher's Exact test is specified. The change in analysis plan stems from the fact that the McNemar's test is designed for paired observations as is the case in this split-face design.

The inflammatory cytokine expression data will be presented as described in the protocol but will due to timing be reported separately from the main CTR.

The analysis of data relating to the microbiome will be specified in a separate analysis plan, and the reporting will be done separately.

The subject's self evaluation of Acne QoL will follow description in the protocol. Item scores will be coded from 0 to 6 with zero most negative and 6 most positive. Four domains are defined by summing item scores as defined in the below table. Missing items will be replaced by the mean of the non-missing data within the same subject, visit and domain. If less than 3 items are scored within a domain the domain sum will be missing.

| Self Perception | | Role-emotional | |
|-----------------|--|----------------|---|
| 1 | Feel unattractive | 5 | Spending time treating face |
| 3 | Feel self-conscious | 9 | Need to have meds or cover-up available |
| 10 | Self-confidence affected | 8 | Meds won't clear face fast enough |
| 2 | Feel embarrassed | 7 | Not looking your best |
| 6 | Dissatisfied with self appearance | 4 | Feel upset |
| Role-Social | | Acne Symptoms | |
| 12 | Going out in public | 15 | Bumps on face |
| 11 | Meeting new people | 16 | Bumps full of pus |
| 14 | Interacting with opposite sex (or same sex if gay) a problem | 17 | Scabbing from acne |
| 13 | Socializing with people a problem | 18 | Concerned with scarring |
| | | 19 | Oily skin |

The subject's self evaluation of TSQM II will follow description in the protocol. Item scores will be coded from 1 to 7 with 1 as the most negative and 7 as the most positive. Four domains are defined by summing item scores as defined in the below table. The domain scores will be scaled from 0 to 100, with 0 as the lowest possible score and 100 as the highest possible score. For domains with 3 items one item may be missing and then the domain score is based on the two non-missing items. For domains with two items both of these must be present for a domain score to be calculated.

| Effectiveness | | Side effects | |
|---------------|---|---------------------|--|
| 1 | How satisfied or dissatisfied are you with the ability of the medication to prevent or treat the condition? | 4 | How dissatisfied are you by side effects that interfere with your physical health and ability to function (e.g., strength, energy levels)? |
| 2 | How satisfied or dissatisfied are you with the way the medication relieves symptoms? | 5 | How dissatisfied are you by side effects that interfere with your mental function (e.g., ability to think clearly, stay awake)? |
| | | 6 | How dissatisfied are you by side effects that interfere with your mood or emotions (e.g., anxiety/fear, sadness, irritation/anger)? |
| Convenience | | Global satisfaction | |
| 7 | How satisfied or dissatisfied are you with how easy the medication is to use? | 10 | How satisfied are you that the good things about this medication outweigh the bad things? |
| 8 | How satisfied or dissatisfied are you with how easy it is to plan when you will use the medication each time? | 11 | Taking all things into account, how satisfied or dissatisfied are you with this medication? |
| 9 | How satisfied or dissatisfied are you by how often you are expected to use/take the medication? | | |

The subject's global cosmetic score will be presented as described in the protocol. The following transformation from the eCRF categories to numerical ratings will be used:

| Category | Rating |
|-------------------|--------|
| Much worsened | 0 |
| Somewhat worsened | 1 |
| No change | 2 |
| Somewhat improved | 3 |
| Much improved | 4 |

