Women of childbearing potential must have a urine pregnancy test performed.

In Cohort 2, 3 and 4, non-invasive samples from the skin will be taken for evaluation of inflammatory markers, skin microbiome profile (For details see Appendix 2 and Appendix 4).

Subjects in Cohort 1, 2 and 3 will be photographed at all site visits from Day 1 and onwards for documentation of physical appearance (Appendix 3). Photographs will be taken at screening for Cohort 3 and 4 for documentation of eligibility.

Each subject will be left/right randomised to receive active treatment on TA_{left} or TA_{right}. The other side will be treated with vehicle gel.

Treatment Phase (Day 1, 2 and 3)

During the treatment phase, trial visits will be performed on Day 1, Day 2 and Day 3.

The individual transparent film(s) will be used to locate the TAs.

LSR scores for the TAs will be recorded and any new or on-going AEs, and changes in medication will be recorded.

Criteria for treatment on Day 2 and Day 3:

- The subject not reporting intolerable response to treatment.
- The (sub)investigator not evaluating LSRs or treatment-related AEs to be unacceptable.
- The LSR scores not exceeding predefined criteria (see Table 1).

Table 1. LSR score criteria for not administering second or third treatment.

LSR component(s)	Score on Day 2 and/or 3
Erosion/ulceration	≥2
Vesiculation/pustulation	≥3
Any LSR component	=4
Flaking/scaling + crusting	≥5 (sum)
Flaking/scaling + crusting + vesiculation/pustulation	≥6 (sum)

The reason not to treat is recorded in the eCRF. Subjects will remain in the trial and attend the follow-up visits according to the protocol.

The IPs are to be applied to the TAs by the site staff as per the randomization schedule at all three treatment visits (Visit 2, 3 and 4). Subjects will be carefully instructed in how long the IP must remain on the skin and how it can be washed off. Moreover, the subjects will be reminded about the precautions regarding accidental transfer of the IP to eyes and other areas (refer to section 10.3.2).

Post-treatment assessment (Day 2, 3, 4 and 8)

If the subject is not treated on Day 2 or Day 3, trial procedures will follow the trial schedule as described in Section 8.1. LSR scores for the TAs will be recorded and any new or ongoing AEs, and changes in medication will be recorded in the eCRF.

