11.3.6.6 Subject evaluation of TSQM II

Descriptive statistics will be provided for the subject's evaluation of TSQM II at Week 12 for the total and each of the four domains contained within the questionnaire (effectiveness, side effects, convenience and global satisfaction).

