A derived score for each of the four dimensions of the TSQM (effectiveness, side effects, convenience, global satisfaction) will be calculated for each subject. For each of the TSQM dimensions the derived score will be summarised using the mean, SD, median, minimum and maximum values at week 12 for each treatment group.

TSQM (Version II): Treatment Satisfaction Questionnaire for Medication

1. How satisfied or dissatisfied are you with the ability of the medication to prevent or treat the condition?

1. Extremely Dissatisfied
2. Very Dissatisfied
3. Dissatisfied
4. Somewhat Satisfied
5. Satisfied
6. Very Satisfied
7. Extremely Satisfied

2. How satisfied or dissatisfied are you with the way the medication relieves symptoms?

1. Extremely Dissatisfied
2. Very Dissatisfied
3. Dissatisfied
4. Somewhat Satisfied
5. Satisfied
6. Very Satisfied
7. Extremely Satisfied

3. As a result of taking this medication, do you experience any side effects at all?

1. Yes
2. No

4. How dissatisfied are you by side effects that interfere with your physical health and ability to function (e.g., strength, energy levels)?

1. Extremely Dissatisfied
2. Very Dissatisfied
3. Somewhat Dissatisfied
4. Slightly Dissatisfied
5. Not at all Dissatisfied

5. How dissatisfied are you by side effects that interfere with your mental function (e.g., ability to think clearly, stay awake)?

1. Extremely Dissatisfied
2. Very Dissatisfied
3. Somewhat Dissatisfied
4. Slightly Dissatisfied
5. Not at all Dissatisfied

6. How dissatisfied are you by side effects that interfere with your mood or emotions (e.g., anxiety/fear, sadness, irritation/anger)?

1. Extremely Dissatisfied
2. Very Dissatisfied
3. Somewhat Dissatisfied
4. Slightly Dissatisfied
5. Not at all Dissatisfied

7. How satisfied or dissatisfied are you with how easy the medication is to use?

1. Extremely Dissatisfied
2. Very Dissatisfied
3. Dissatisfied
4. Somewhat Satisfied
5. Satisfied
6. Very Satisfied
7. Extremely Satisfied

8. How satisfied or dissatisfied are you with how easy it is to plan when you will use the medication each time?

1. Extremely Dissatisfied
2. Very Dissatisfied
3. Dissatisfied
4. Somewhat Satisfied
5. Satisfied
6. Very Satisfied
7. Extremely Satisfied

9. How satisfied or dissatisfied are you by how often you are expected to use/take the medication?

1. Extremely Dissatisfied
2. Very Dissatisfied
3. Dissatisfied
4. Somewhat Satisfied
5. Satisfied
6. Very Satisfied
7. Extremely Satisfied

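### TSQM II: the SAP's 1-to-7 item coding does not fit the five-option Side effects items, and Appendix 12's summary by treatment group cannot be produced from one questionnaire per subject

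*SAP*

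**What the plan says.** **Coding and scaling.** For the TSQM II, SAP section 4.3.2 states: "Item scores will be coded from 1 to 7 with 1 as the most negative and 7 as the most positive". It makes no exception for any item. Its domain table assigns items 4, 5 and 6 to Side effects. On scaling it says: "The domain scores will be scaled from 0 to 100, with 0 as the lowest possible score and 100 as the highest possible score". On missing items: "For domains with 3 items one item may be missing and then the domain score is based on the two non-missing items". No formula is written out.

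**Questionnaire.** In protocol Appendix 12, items 1, 2, 7, 8 and 9 have seven response options. Items 4, 5 and 6 have five, and the most favourable is "5. Not at all Dissatisfied".

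**Summary.** Appendix 12 derives one score per dimension for each subject and then asks for summary statistics including "minimum and maximum values at week 12 for each treatment group". Protocol section 11.3.6.6 plans descriptive statistics only and does not mention treatment. SAP section 4.3.2 says the TSQM II evaluation follows the protocol.

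**Design.** Protocol section 6.1 describes an intra-individual split-face trial. Each subject is randomised to active gel on one cheek, and "The other side will be treated with vehicle gel". Under section 8.14 and the schedule in section 8.1, the TSQM II is completed once, at Week 12.

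**The concern.** The coding rule cannot be applied as written to one of the four domains. Nobody can tick a sixth or seventh option on items 4 to 6, and the SAP does not say how five options become codes from 1 to 7. A programmer who keeps the printed codes but takes the item range from the SAP sentence would understate the whole Side effects domain. That domain would also sit on a different scale from Convenience, the other three-item domain, whose items do have seven options.

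The second problem lies in the unit of analysis. A score that exists once per subject cannot be divided between two gels that every subject received. If the Appendix 12 wording were carried into the tables, the output would either be impossible to fill or would label something else as a treatment comparison.

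**Working it through.** **Inputs**
- Item range stated for all items: 1 to 7 (SAP 4.3.2).
- Options printed for items 4 to 6: five, coded 1 to 5 (Appendix 12).
- Stated limits of the domain score: 0 and 100 (SAP 4.3.2).
- Items needed for Side effects: three, or two if one is missing (SAP 4.3.2).
- Assumption: scaling is linear, score = 100 × (S − k × min) / (k × (max − min)), where S is the sum of the k answered items. The SAP gives no formula.

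**Step 1: reproduce the stated range where the coding fits.** Effectiveness has two seven-option items. The lowest sum gives (2 − 2)/12 × 100 = 0 and the highest gives (14 − 2)/12 × 100 = 100. The stated 0 to 100 is met.

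**Step 2: Side effects, three items answered.** The 1-to-7 range gives (S − 3)/18 × 100. The attainable 1-to-5 range gives (S − 3)/12 × 100.

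| Answer to all three items | S | Printed codes on 1-to-7 range | Attainable range |
|---|---|---|---|
| 1 | 3 | 0 | 0 |
| 2 | 6 | 16.7 | 25 |
| 3 | 9 | 33.3 | 50 |
| 4 | 12 | 50.0 | 75 |
| 5 | 15 | 66.7 | 100 |

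The stated maximum of 100 is not reached in the third column.

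**Step 3: two items answered.** The 1-to-7 range gives (S − 2)/12 × 100, so S = 2, 6, 10 gives 0, 33.3, 66.7. The attainable range gives (S − 2)/8 × 100, so the same sums give 0, 50, 100.

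**Step 4: size of the error.** The ratio is 12/18 = 0.667 with three items and 8/12 = 0.667 with two. It is the same for every answer pattern above the minimum, and the minimum is 0 on both scales. The mean, SD, median, minimum and maximum of the domain are therefore all multiplied by 0.667.

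**Step 5: an even spread over 1 to 7.** Recode the five options as 1, 2.5, 4, 5.5, 7. Each step is then 1.5, and the score is 1.5 × (S − 3)/18 × 100 = (S − 3)/12 × 100. This is identical to the attainable-range score, so the error is zero.

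**Step 6: the split by gel.** No arithmetic applies, so the texts are set side by side.
- Each subject has one cheek on active gel and the other on vehicle (section 6.1).
- Each subject completes one TSQM II, at Visit 10 (section 8.14).
- The visible items do not refer to a side of the face. Item 1 reads: "How satisfied or dissatisfied are you with the ability of the medication to prevent or treat the condition".
- The Subject Global Cosmetic Score form in Appendix 5 has separate right and left sections, so its summary by treatment in section 11.3.6.7 is feasible. The visible TSQM II has no such sections.

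Each subject thus gives one answer covering two gels. Grouping subjects by which cheek was randomised to active gel would not compare treatments either, since both groups received both gels.

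**The case against.** **On coding.** The SAP fixes the end points twice: the most positive answer is coded 7, and the best possible domain score is 100. A programmer who respects either statement gets 100 for the best answers. The 66.7 ceiling needs a programmer to keep 5 as the top code and still divide by a range that ends at 7, which conflicts with both. This stands, and it makes the two-thirds factor a conditional programming risk. A reader might infer that the reported Side effects scores will be one third too low. The documents do not support that, because they do not show which scaling is programmed. What remains is that the SAP gives neither the intermediate codes nor a formula, and its one coding sentence does not match the form. The double programming of analysis data sets in SAP section 5 lowers the risk but does not remove it, since both programmers read the same sentence.

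**On the split by gel.** Section 11.3.6.6 does not ask for it and the SAP does not add it, so the Appendix 12 phrase may be leftover wording with little effect. That is fair as to impact. However, the SAP refers back to the protocol for this endpoint without settling the conflict. In the same section it does correct another analysis for the paired design, replacing Fisher's exact test with McNemar's test.

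**On the total.** Section 11.3.6.6 promises statistics on "evaluation of TSQM II at Week 12 for the total and each of the four domains", while the visible texts of Appendix 12 and the SAP derive only four scores. A reader might infer that the total is undefined. That cannot be claimed, because part of the appendix text is not available for review and the SAP defers to the protocol.

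**Conclusion.** Two wording faults hold, and both are minor.

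1. The 1-to-7 coding rule does not fit the Side effects items. The error is a factor of 0.667 on every summary of that domain if printed codes are scaled on 1 to 7. It is zero if the attainable range or an even spread over 1 to 7 is used. This assumes linear scaling.
2. The Appendix 12 summary by treatment group is impossible with one subject-level questionnaire in a split-face design. This rests on the single completion in section 8.14 and on the wording of the items that can be seen.

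The response options of items 10 and 11 and the separate table shells could not be checked. TSQM II is an exploratory endpoint (protocol section 5.3) with descriptive statistics only, so no test and no part of the primary analysis depends on it.

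**What to change.** Make both changes in the SAP. Protocol section 11.3.11 allows changes to the planned analysis to be described and justified there.

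- Code items 4 to 6 as 1 to 5. Write out the Side effects score as (sum − 3)/12 × 100 with three items answered and (sum − 2)/8 × 100 with two. Coding the five options as 1, 2.5, 4, 5.5 and 7 on the 1-to-7 range is equivalent, provided it is written down.
- State that TSQM II is summarised once over all subjects, labelled as the combined split-face experience, and not by gel. Note that this departs from the Appendix 12 wording.

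The cost is a few sentences of text. Data collection does not change.

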8.14 Subject Reported Outcomes

The subject must complete Acne-QoL at Visit 2 (Day 1) and Visit 10 (Week 12, End of Trial).

The subject must complete TSQM II and Subject Global Cosmetic Score at Visit 10 (Week 12, End of Trial).

Subject-reported outcome measures should be completed prior to any other assessments at the respective trial visits in the following order: Acne QoL, TSMQ II and Subject Global Cosmetic Score. The subjects should be encouraged to answer all questions in the questionnaires.

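### The TSQM II Side effects score ignores item 3, so a subject who reports no side effects and leaves items 4–6 blank is scored missing

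*SAP*

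**What the plan says.** The questionnaire in Protocol Appendix 12 first asks, with Yes or No as the answers: "3. As a result of taking this medication, do you experience any side effects at all". Items 4 to 6 then ask about dissatisfaction caused by side effects. Item 4, for example, reads "How dissatisfied are you by side effects that interfere with your physical health and ability to function (e.g., strength, energy levels". Each of these items has five responses, the best being "5. Not at all Dissatisfied". The printed text carries no instruction to skip them after a No.

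On scoring, SAP 4.3.2 says "Four domains are defined by summing item scores as defined in the below table". That table gives Side effects items 4, 5 and 6, and item 3 appears under none of the four domains. Domain scores run from 0 to 100. On missing answers: "For domains with 3 items one item may be missing and then the domain score is based on the two non-missing items". Neither document says what a No on item 3 means for the score.

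Appendix 12 plans a derived score on each dimension for every subject. On completion, Protocol 8.14 says "The subject must complete TSQM II and Subject Global Cosmetic Score at Visit 10 (Week 12, End of Trial", and also "The subjects should be encouraged to answer all questions in the questionnaires".

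**The concern.** The wording of items 4–6 presupposes that there are side effects to be dissatisfied with. A subject who has just answered No may reasonably leave them blank, and the SAP then gives no score. The loss is informative: those most likely to drop out of the domain are those with nothing to complain about. Two subjects with the same experience can also be treated differently, one scored at the top for ticking the best box three times and one missing for leaving the boxes empty.

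The timing makes No a plausible answer. The form is given at Week 12, after at most three days of dosing, and Protocol 3.4 describes local reactions as typically resolving in 2–4 weeks. That description comes from actinic keratosis subjects over 40, and the same section says responses in this population may differ. The share answering No is therefore unknown.

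At stake is the direction of one descriptive summary and the number of subjects behind it. No test or decision in the trial depends on it.

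**Working it through.** The plan gives no figure on this point to reproduce. The check applies the SAP rule to the possible answer patterns and then works out what the rule does to the mean.

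**Inputs from the documents**
- Side effects domain: items 4, 5 and 6, with at least two answered (SAP 4.3.2).
- Five printed responses per item, 5 being best (Protocol Appendix 12).
- Domain scale 0 to 100 (SAP 4.3.2).
- 38 subjects, the planned full analysis set (Protocol 11.2), used for illustration.

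**Assumptions, not in the documents**
- p: share of subjects who answer No on item 3 and end up without a score.
- m: mean score among the scored subjects, taken as 50 to 75.
- The right score for a No without a domain score is 100, the top of the scale.

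**Step 1: the scoring rule.** With k answered items and responses 1 to 5, score = 100 × (sum − k) / (k × (5 − 1)), defined only if k is at least 2.

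| Items 4, 5, 6 | Score |
|---|---|
| 5, 5, 5 | 100 × (15 − 3) / 12 = 100 |
| blank, 5, 5 | 100 × (10 − 2) / 8 = 100 |
| blank, blank, 5 | missing |
| all blank | missing |

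Item 3 changes none of these results. A No with two or three blanks is missing; a No with three best answers scores 100 and stays in the summary.

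**Step 2: the bias.** Reported mean = m. Mean with the lost subjects scored 100 = 100p + m(1 − p). Bias = m − [100p + m(1 − p)] = −p(100 − m).

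**Step 3: the size, with 38 subjects**

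| Lost | p | Contributing n | Bias, m = 50 | Bias, m = 75 |
|---|---|---|---|---|
| 0 | 0 | 38 | 0 | 0 |
| 4 | 4/38 = 0.105 | 34 | −5.3 | −2.6 |
| 10 | 10/38 = 0.263 | 28 | −13.2 | −6.6 |
| 19 | 19/38 = 0.500 | 19 | −25.0 | −12.5 |

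**Step 4: a milder case.** Suppose 10 subjects answer No, 5 leave items 4–6 blank, 5 tick the best response throughout, and the 28 Yes subjects average 50. The reported mean is (28 × 50 + 5 × 100) / 33 = 57.6. With all 10 at 100 it is (28 × 50 + 10 × 100) / 38 = 63.2, a bias of −5.6. If the Yes subjects average 75, the bias is −2.8.

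**Step 5: dependence on the coding.** SAP 4.3.2 codes TSQM items 1 to 7, but items 4–6 have five responses. Scaled literally on 1–7, three best answers give 100 × (15 − 3) / (3 × 6) = 66.7. A score of 100 for a No is on the same footing as the other scores only if items 4–6 are scaled on 1–5.

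**The case against.** A reader might infer that the summary would describe only subjects with side effects. The documents do not support that. It would require every No subject to leave at least two of items 4–6 blank, whereas the visible form has no skip instruction, offers a best response that a subject without side effects can tick, and comes with directions in Protocol 8.14 to complete it and to encourage all answers. A subject who follows those directions is scored correctly. A form instruction or data-entry rule could also sit in text not available here. This objection stands, and the point is conditional for that reason.

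The size can fairly be challenged too. Items 4–6 concern physical function, mental function and mood, while the expected reactions are local, so Yes subjects may also score high. With m = 90 and p = 50% the bias is only −0.5 × 10 = −5 points. Nor is 38 a forecast of Week 12 forms: Protocol Appendix 1 plans 30 completers.

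Finally, tolerability is covered by the adverse event and local skin response summaries, which do not use TSQM II. That limits the importance of the point.

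What remains is the scoring gap. Encouragement to answer does not say how blanks are scored, and the SAP itself expects some items to be missing.

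**Conclusion.** The concern holds in conditional form. Under SAP 4.3.2 a No on item 3 with two or more of items 4–6 blank gives a missing Side effects score, at odds with the protocol's intention to score every subject. To the extent it occurs, the reported mean is biased towards dissatisfaction by p(100 − m) and rests on fewer subjects.

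For 38 subjects and an assumed m of 50 to 75, the shift is about 3–5 points with 4 subjects lost, 7–13 with 10 and 13–25 with 19. It is zero if every No subject ticks the best response. How many would be lost cannot be determined from the documents, and treating a No as 100 is a reasonable convention that they do not state.

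TSQM II is an exploratory endpoint with descriptive analysis only (Protocol 5.3 and 11.3.6.6), so this is a minor point that is worth correcting because it is cheap.

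**What to change.** Add to SAP 4.3.2:

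- If item 3 is No and fewer than two of items 4–6 are answered, set the Side effects score to 100, the highest possible score.
- In all other cases, including item 3 blank, apply the existing rule to items 4–6, scaled on the printed 1–5 range.
- Report the item 3 Yes/No counts and the contributing n beside the domain summary.

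The rule should not restrict items 4–6 to subjects who answered Yes. That would leave subjects with item 3 blank unscored and would override real answers from No subjects who completed items 4–6.

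The cost is one sentence and one derivation line, using data already collected, and the score will show a visible ceiling at 100. Protocol 11.3.11 provides the route: an SAP update, preferably before unblinding, or otherwise a justified change described in the clinical trial report.
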